6.7 Echocardiography

An echocardiogram will be performed at the screening visit as well as the 1 month visit. Echocardiography will be performed to measure the size and shape of the heart, its chambers and blood flow as well as valvular structure and function. Additionally, the echocardiogram will be used for detection of any wall motion abnormalities indicative of myocarditis.

The quantitative echocardiographic data points must include:

- End Diastolic Volume
- End Systolic Volume
- Ejection Fraction
- LV End Systolic Diameter
- LV End Diastolic Diameter

6.8 24 Hour Ambulatory ECG Monitor

A 24 hour ambulatory ECG monitor will be performed at the screening visit, during the 24 hours following release (discharge) from the hospital and also at the 1 month, 6 months and 12 months study visits. Subjects enrolled in the Safety Cohort will also have the test performed at the 2 months study visit. The monitor is used to detect and record arrhythmia. All changes and any associated clinical significance will be evaluated and documented on the case report form.

6.9 Magnetic Resonance Imaging Protocol

With the exception of those subjects who develop MRI contraindications, all subjects will undergo contrast-enhanced MRI at screening and the months 6 and 12 study visits. Study imaging sites must be trained and certified specifically for this protocol prior to conducting cardiac MRI in subjects with ICD and/or pacemaker placement. The imaging protocol will first include sagittal, axial and oblique scout images to localize the heart. It is anticipated that the duration of each MRI session will be 45-60 minutes. Acquisition parameters and techniques will be protocolled and the site-based MRI technicians will be trained and certified in the common acquisition protocol prior to initiation of enrollment at each site.

6.9.1 Cine Imaging Protocol

A cine imaging protocol will be utilized for global ejection fraction and LV volumes and mass determination. Acquisition parameters and techniques will be protocolled and the site-based MRI technicians will be trained and certified in the common acquisition protocol prior to initiation of enrollment at each site.

6.9.2 Delayed Contrast-Enhancement Protocol

This is the most accurate assessment of infarct scar size. Subjects will receive a total bolus intravenous injection of 0.2 mmol/kg of gadolinium contrast as long as GFR is > 60 mL/min (for GFR 30-60 mL/min, 0.15 mmol/kg will be given; subjects whose GFR declines to <30 during the study period will be excluded from contrast injections during subsequent MRI studies). High-resolution delayed enhancement images will be obtained using an inversion- recovery prepared gated fast gradient echo pulse sequence.

6.9.3 Image Analysis

All study images and applicable imaging data will be sent to and centrally read at an independent imaging core by cardiovascular radiology experts. MRI will be performed on standard phantoms for quality assurance and to detect any changes in system sensitivity over time.

6.10 Chest, Abdomen and Pelvis CT

A computerized tomography (CT) of the chest, abdomen and pelvis will be performed at the screening visit to ensure that there are no clinically significant pre-existing abnormalities to internal organs or presence of tumors or cancer. The CT will be performed with contrast. If any

abnormalities are found that affect the subject's participation in the study, the subject will be withdrawn from the study as a screen failure and not followed further. The subject must continue to meet all inclusion and no exclusion criteria in order to continue in the study.

6.11 Clinical Function and Quality of Life Measures

At the screening, 6 month and 12 month study visits, the subject will be asked to complete the Minnesota Living with Heart Failure Questionnaire (MLHFQ), the Short Form-36 health survey (SF-36), the Work Productivity and Activity Impairment Questionnaire: Specific Health Problem (WPAI:SHP), and to make a global assessment of the improvement or worsening of his/her condition (Patient Global Assessment).

In addition, subjects will perform a Six Minute Walk test at screening, and at the 6 and 12 month study visits. New York Heart Association (NYHA) functional status will be evaluated at screening, 1 month, 3 months, 6 months and 12 months study visits.

7 STUDY ACTIVITIES

The Schedule of Events for the conduct of this study is shown in [Appendix 1](#).

Subjects may sign consent and start the screening process immediately post-MI (e.g., acute admission at hospital). The following assessments will be permitted within 28 days immediately following the subject's MI: signing ICF, review of medical history, review of concomitant medications, and collection of laboratory samples required for assessment of study eligibility criteria (e.g., eGFR, HbA1c, hepatitis serology, HIV serology, LFTs, hematocrit, WBC, and platelet count). All other screening tests, including the subject's cardiac MRI and CT (chest, abdomen, pelvis), must be conducted greater than 28 days post-MI. Infusion must occur within 28 days of the first screening procedure that is performed greater than 28 days post-MI. Relevant safety laboratory sample collections (e.g., chemistry, hematology, urinalysis) may need to be repeated as they must be obtained within 28 days of the subject's infusion. A subject that rescreens for any reason may be required to repeat all protocol safety procedures (excluding CT of the chest, abdomen and pelvis if previously conducted) if the safety procedures were originally conducted greater than 28 days prior to the subject's infusion. A subject that rescreens for any reason may be required to repeat all protocol efficacy procedures including the cardiac MRI unless: a) the subject's efficacy procedures including baseline cardiac MRI were conducted within 28 days of infusion; **or**, b) the subject's efficacy procedures including baseline cardiac MRI were conducted \geq 60 days post-MI **and** within 60 days of infusion. After completion of the screening procedures and meeting all inclusion and exclusion criteria, study subjects will be randomized to receive CAP-1002 or placebo administered via intracoronary infusion. Study subjects will undergo catheterization and infusion on the day of admission and will be observed in the hospital with continuous cardiac monitoring overnight, 20 to 24 hours afterwards. In the absence of serious adverse events, subjects will be discharged the day after catheterization, with a 24-hour ambulatory ECG monitor.

7.1 Screening Period

No screening exams will take place until the subject is fully informed of the research and signs the informed consent. Subjects may sign consent and start the screening process immediately post-MI (e.g., acute admission at hospital). The following assessments will be permitted within 28 days immediately following the subject's MI: signing ICF, review of medical history, review of concomitant medications, and collection of laboratory samples required for assessment of study eligibility criteria (e.g., eGFR, HbA1c, hepatitis serology, HIV serology, LFTs, hematocrit, WBC, and platelet count). All other screening tests, including the subject's cardiac MRI and CT (chest, abdomen, pelvis), must be conducted greater than 28 days post-MI. Relevant safety laboratory sample collections (e.g., chemistry, hematology, urinalysis) may need to be repeated as they must be obtained within 28 days of the subject's infusion.

Screening tests and procedures include:

- Medical history, limited physical examination, and cardiac physical examination
- Medication review
- Vital Signs
- 12-Lead ECG
- Laboratory tests: HLA typing, DSA evaluation
- Echocardiography
- Cardiac MRI
- Laboratory tests: hematology, chemistry, urinalysis, hemoglobin A1c (HbA1c), serum NT-proBNP, Serum β -HCG (only for females who are not diagnosed as postmenopausal), HIV and hepatitis screens, ELISpot Assay sample; refer to [Table 1](#) for comprehensive list of laboratory tests
- Serum for biomarkers (if subject has provided consent)
- 24 hour ambulatory ECG monitoring
- NYHA functional class assessment
- Six Minute Walk Test
- MLHFQ
- SF-36 health survey
- WPAI:SHP questionnaire
- Patient Global Assessment
- Adverse event assessment
- CT of the chest, abdomen and pelvis [note: the subject's CT of the chest, abdomen, and pelvis should be conducted after all other screening study eligibility criteria have been met, including independent imaging core confirmation of baseline (screening) MRI eligibility]

A subject that rescreens for any reason may be required to repeat all protocol safety procedures (excluding CT of the chest, abdomen and pelvis if previously conducted) if the safety procedures were originally conducted greater than 28 days prior to the subject's infusion. A subject that rescreens for any reason may be required to repeat all protocol efficacy procedures including the

cardiac MRI unless: a) the subject's efficacy procedures including baseline cardiac MRI were conducted within 28 days of infusion; **or**, b) the subject's efficacy procedures including baseline cardiac MRI were conducted \geq 60 days post-MI **and** within 60 days of infusion.

Protocol safety procedures are defined as:

- Medical history, limited physical examination, and cardiac physical examination
- Medication review
- Vital signs
- 12-Lead ECG
- Laboratory tests: hematology, chemistry, urinalysis, hemoglobin A1c (HbA1c), serum NT- proBNP, Serum β - HCG (only for females who are not diagnosed as postmenopausal), HIV and hepatitis screens, and serum for biomarkers (if subject has provided consent); refer to [Table 1](#) for comprehensive list of laboratory tests
- 24 hour ambulatory ECG monitoring
- Adverse event assessment

Protocol efficacy procedures are defined as:

- Laboratory tests: serum NT- proBNP HLA typing, DSA evaluation, ELISpot Assay sample
- Echocardiography
- Cardiac MRI
- NYHA functional class assessment
- Six Minute Walk Test
- MLHFQ
- SF-36 health survey
- WPAI:SHP questionnaire
- Patient Global Assessment

Randomization will occur after all of the screening examinations have been completed and only if the subject continues to meet all of the eligibility criteria. After the subject is randomized, the subject must continue to meet eligibility criteria before proceeding to intracoronary infusion.

Sites should randomize eligible subjects at least three (3) working days **prior** to a subject's scheduled infusion date. The Sponsor should be notified of cases that prevent randomization at least three (3) working days prior to a subject's scheduled infusion date (e.g., timing of MRI results). Subjects who are not randomized and do not proceed to infusion due to violation of eligibility criteria at screening will be withdrawn from the study as screen failures and will have no further follow up.

7.2 Treatment Period

7.2.1 Intracoronary Infusion Visit (Day 0)

Intracoronary infusion of CAP-1002 or placebo must occur within 28 days of the first screening procedure that is performed greater than 28 days post-MI. At the infusion visit, subjects will be clinically stable as judged by no evidence of infection, stable blood pressure and pulse, as well as over the prior four days by history no change in angina pattern, or in angina or heart failure medications.

As part of the infusion visit, subjects will undergo the following tests and assessments:

Pre-infusion:

- Medical history and cardiac physical examination
- Medication review
- Vital signs
- 12-Lead ECG
- Laboratory tests: hematology, chemistry, urinalysis, serum NT-proBNP, and INR/PTT [as needed for subjects on warfarin (Coumadin®)]; refer to [Table 1](#) for comprehensive list of laboratory tests
- Cardiac enzymes (Serum troponin and CK-MB)

Post-infusion:

- Cardiac assessment
- Vital signs approximately every 8 hours (from infusion time) until discharge
- Cardiac enzymes (serum troponin and CK-MB) approximately every 8 hours x3 with last blood draw immediately prior to discharge (20-24 hours post infusion)
- Urinalysis
- 12-Lead ECG (day of discharge)
- 24 hour ambulatory ECG monitoring (apply to subject immediately prior to discharge)
- Adverse Event assessment

Subjects must have a patent coronary artery with TIMI flow 3 in order for the IP to be infused. Subjects with angiographic evidence of a coronary occlusion determined to be clinically significant, with or without clinical symptoms during the day of IP infusion: 1) will not undergo intracoronary infusion of the IP, 2) will be withdrawn from the study, and 3) will not be followed further for either safety or efficacy. The decision to attempt opening and restoration of TIMI-3 flow will be based on clinical grounds.

Stopping criteria that would trigger halting of the CAP-1002 or placebo infusion are:

1. Sustained hypotension unresponsive to fluids and/or medications.
2. Evidence of acute coronary syndrome.
3. Development of TIMI flow 0/1, after a cycle of infusion.
4. Evidence of cerebrovascular accident.
5. Evidence of cardiac tamponade.
6. Hemopericardium requiring pericardiocentesis.
7. Sustained ventricular tachycardia/ventricular fibrillation that require cardioversion or administration of an antiarrhythmic.
8. Evidence of thrombus in the aorta that was not previously seen on imaging studies.
9. Suspected or confirmed aortic dissection.
10. Suspected or confirmed coronary dissection.

11. Acute onset of rigors (symptoms indicative of acute sensitivity or infection).
12. Sustained ST-segment elevation or angina symptoms which persist longer than the time the balloon is deflated (> 3 minutes) with angiographic evidence of microvascular obstruction (i.e., no reflow).

Following intracoronary infusion, subjects will be observed in the hospital for 20-24 hours with continuous cardiac (telemetry) monitoring. Troponin and CK-MB laboratory studies will be monitored every 8 hours from the end of the infusion. A total of three sets of cardiac enzymes will be evaluated to rule out cardiac injury during the post-infusion hospital stay through discharge. If the subject is discharge prior to 24 hours, cardiac enzymes will be drawn just prior to discharge.

Prior to discharge from the hospital, a physical assessment will be performed which will include chest pain assessment, review of laboratory results, ECG, and arterial puncture site as well as assessment of adverse events. In the absence of serious adverse events, subjects will be discharged the day after infusion with a 24 hour ambulatory ECG monitor.

The timing of follow-up visits is based on the date of actual or planned IP administration. Following intracoronary infusion, a subject visit schedule listing target dates for assessments can be printed from the EDC system.

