9.5.2 Primary Efficacy

The primary efficacy objective is to determine if the administration of CAP-1002 by intracoronary infusion may result in structural cardiac benefits for subjects with ischemic left ventricular dysfunction and a previous MI as measured by the percent change from baseline in the MRI assessment of infarct size as a percent of left ventricular mass at 12 months post administration. Baseline assessments are conducted during the “Screening” visit, prior to the administration of CAP-1002 or placebo.

The primary efficacy hypothesis is that CAP-1002 is superior to placebo in reducing infarct size in either all subjects combined (“full group”) or in subjects with recent MI (“subgroup”). A closed testing procedure will be used so that strong control of type 1 error is maintained. Specifically, the following hypothesis sets will be tested:

$$1) \quad \begin{array}{lll} H_{0,s}: \mu_{c,s} - \mu_{p,s} = 0 & \text{or} & H_{0,f}: \mu_{c,f} - \mu_{p,f} = 0 \\ H_{a,s}: \mu_{c,s} - \mu_{p,s} < 0 & & H_{a,f}: \mu_{c,f} - \mu_{p,f} < 0 \end{array}$$

and

$$2) \quad \begin{array}{ll} H_{0,s} \cap H_{0,f}: \mu_{c,s} - \mu_{p,s} = 0 \text{ and } \mu_{c,f} - \mu_{p,f} = 0 \\ H_{a,s} \cap H_{a,f}: \mu_{c,s} - \mu_{p,s} < 0 \text{ or } \mu_{c,f} - \mu_{p,f} < 0 \end{array}$$

where s denotes the subgroup, f denotes the full group, $\mu_{c,s}$ and $\mu_{p,s}$ are mean percent changes in the CAP-1002 and placebo treatment groups, respectively, in the subgroup, and $\mu_{c,f}$ and $\mu_{p,f}$ are mean percent changes in the CAP-1002 and placebo treatment groups, respectively, in the full group.

Therefore, both the intersection null hypothesis ($H_{0,s} \cap H_{0,f}$) and either of the individual null hypotheses ($H_{0,s}$ or $H_{0,f}$) must be rejected at the (one-sided) 0.025 significance level for the trial to be declared a success. In other words, the null hypothesis of “no treatment effect in the full group and no treatment effect in the recent MI subgroup” must be rejected at the one-side 0.025 significance level, necessarily meaning that either the result is significant in the full group, in the recent MI subgroup, or both. The results of the tests of the individual hypotheses (also at the one-sided 0.025 significance level) determines which specific comparisons are significant.

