9.6.2 Secondary Efficacy

All comparisons in the secondary analyses will be based on a null hypothesis of no difference in the endpoint between subjects administered CAP-1002 as compared to placebo and an alternate hypothesis of a difference in the endpoint for subjects administered CAP-1002 as compared to placebo. Secondary analyses will be based on a random effects model similar to the primary but will be based on an alpha of 0.05 without controlling for multiplicity.

The following secondary efficacy endpoints will be evaluated during the six-month and twelve-month follow-up periods:

Global LV Function measures

1. Percent change and change from baseline in MRI assessment of LVEF
2. Percent change and change from baseline in MRI assessment of left ventricular end-diastolic and end-systolic volumes indexed to BSA

Structural measures

3. Change from baseline in MRI assessment of infarct size as a percent of left ventricular mass
4. Percent change and change from baseline in MRI assessment of infarct size expressed in grams
5. Percent change and change from baseline in MRI assessment of viable mass expressed in grams

Regional measure

6. Percent change and change from baseline in MRI assessment of function in the region which received CAP-1002 therapy

Clinical function/status measures

7. Changes from baseline in distance covered in six minute walk test

8. Change from baseline in Minnesota Living with Heart Failure Questionnaire (MLHFQ) score
9. Change from baseline in SF-36 score
10. Change from baseline in WPAI:SPH score
11. Change from baseline in Patient Global Assessment (PGA) score
12. Change from baseline in NYHA Class

Biomarker

13. Percent change and change from baseline in NT-proBNP
14. Change from baseline in log transformed NT-proBNP

Additional detail regarding secondary endpoint analyses can be found in the SAP.

Analyses of the secondary efficacy endpoints will be performed using the same longitudinal modeling approach as the primary efficacy endpoint; the baseline covariate used in the model will be the baseline of the endpoint being analyzed. Two-sided testing will be performed at level $p=0.05$.

A correlational analysis will be presented (for tissue based and functional measures) with Pearson's correlation coefficient for all possible pairs of efficacy endpoints and where appropriate the Spearman's correlation coefficient will be presented.

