## 7.6 Study Period and Time Point Definitions

The following study periods and time points are defined:

Screening Period: the 4-week time period before IP infusion.

Baseline: the last observation of a given parameter before IP infusion of a given subject.

Day 0: the day of planned IP infusion of a given subject.

(Nominal Visit) Analysis Time Point: analysis based on data collected at the *(nominal visit)* time point, where nominal visits are as shown in the table below.

EOS, Subject Level: subject-level EOS is reached after completion of the Month 12 visit or study or discontinuation for any reason.

EOS, Study-Level: study-level EOS is reached when all randomized subjects have either completed the Month 12 visit or have discontinued from the study for any reason.

Long-Term Follow-Up (LTFUP) Period, Subject-Level: the LTFUP period begins after completion of the Month 12 visit and continues until 4 more annual visits have been completed.

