## 9. EFFICACY ANALYSIS

All efficacy parameters will be listed for the primary ITT population and summarized for the mITT population. The primary analysis of primary and secondary efficacy endpoints will be done using the primary mITT population. Secondary analyses may be done using the other analysis populations defined in [Section 6](#) or in subgroups defined in [Section 7.4](#). In addition, “last observation” analyses will be done for certain parameters for which some subjects’ final assessments were done too late to be included in the Month 12 analysis window.

Analyses of changes from baseline will be done using general linear models with baseline values as covariates. Analyses of the effect of treatment group, analysis window (e.g., baseline, Month 6, Month 12), and their interaction will be done using mixed effects linear regression, with subject as a random effect, analysis window, and treatment group as fixed effects, and baseline as a fixed-effect covariate. For “last observation” analyses, “time” as a continuous covariate will be substituted for analysis window. Study site may also be included as a random effect if there is evidence of correlation within study sites (per the interclass correlation coefficient from the unconditional model) and/or if doing so appreciably improves the model fit (e.g., per Akaike’s Information Criterion). Other covariates that may be considered include age (< 65 vs.  $\geq$  65 years), sex, race (African-American vs. other), baseline 6MWT, baseline LVESV, baseline NT-proBNP, and DSA (as an indicator variable). Residuals will be evaluated for substantial departure from normality and independent and constant variance and appropriate remedies (e.g., data transformations, detecting and assessing the influence of outliers, alternative analytical approaches) will be attempted when necessary. An unstructured covariance will be the default covariance structure but other structures (e.g., compound symmetry) may be used to evaluate sensitivity to the choice of structure or, if study site is included as a random effect, to achieve convergence.

Assuming missing observations are “missing at random” (MAR), i.e., the fact that they are missing is unrelated to the missing variable but can be related to another variable on which data have been collected, the maximum likelihood (ML) approach is able to handle subjects with

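### NT-proBNP is drawn twice before infusion but the secondary model adjusts for one value only; entering both would cut residual variance by about 0 to 20%, depending on correlations the documents do not give

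*Protocol*

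**What the plan says.** **Two pre-infusion measurements.** The screening laboratory list in Protocol 7.1 includes "hematology, chemistry, urinalysis, hemoglobin A1c (HbA1c), serum NT-proBNP". The pre-infusion list for Day 0 in Protocol 7.2.1 reads "Laboratory tests: hematology, chemistry, urinalysis, serum NT-proBNP, and INR/PTT". Appendix 1 of the protocol marks NT-proBNP at both times. The interval is normally four weeks or less, because infusion "must occur within 28 days of the first screening procedure that is performed greater than 28 days post-MI"; the rescreening rules can make it longer.

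**One baseline in the model.** Protocol 9.6.2 says that "the baseline covariate used in the model will be the baseline of the endpoint being analyzed". SAP 9 likewise specifies "baseline as a fixed-effect covariate". SAP 7.6 defines baseline as "the last observation of a given parameter before IP infusion of a given subject", which for NT-proBNP is the Day 0 sample. SAP 9 lists baseline NT-proBNP among the covariates that may be considered, but under the SAP 7.6 definition that is the same single value. Neither document averages the two values or enters both.

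**Endpoint scale.** Protocol 2.4.1 and 9.6.2 list change in NT-proBNP on the original scale, percent change, and change after log transformation. SAP 2.3.6 and 9.5 describe absolute and percent change only.

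**The concern.** A second pre-treatment measurement of the same marker is prognostic for later values. Any single NT-proBNP value carries short-term variation, and a second reading recovers part of what the first misses. Both readings precede infusion, so treatment cannot affect either, and both will be in the database for most subjects. Leaving one out gives up precision that costs no visit, sample or site effort.

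What is at stake is the width of the confidence interval for one secondary endpoint in a trial that plans 93 completers at 2:1. Prespecification also matters. SAP 9 leaves the choice of further covariates open, so a second NT-proBNP covariate added after unblinding could look data-driven.

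**Working it through.** The documents state no variance, correlation, effect size or power for NT-proBNP, so there is no figure of the plan to reproduce. The check compares residual variances, on the log scale with unit variance, at one follow-up visit.

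**Inputs**
- From the documents: two pre-infusion values, one baseline covariate, and 93 completers at 2:1 (about 62 and 31).
- Assumed: ρ, the correlation of a pre-infusion value with the follow-up value, and q, the correlation of the two pre-infusion values with each other.

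**Formulas.** Once Day 0 is a covariate, change from Day 0 and the follow-up value have the same residual variance.
- Day 0 only: 1 − ρ².
- Both values as separate covariates: 1 − (ρ_S² + ρ_D² − 2qρ_Sρ_D)/(1 − q²), where S is screening and D is Day 0. If ρ_S = ρ_D = ρ, this becomes 1 − 2ρ²/(1 + q).
- Change from Day 0 with the mean of the two as the only covariate, all correlations equal to r: 2(1 − r) − (1 − r)²/(2(1 + r)).

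**Case 1: all correlations equal (q = ρ = r)**

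| r | Day 0 only (current plan) | Both values | Cut in residual variance | Change from Day 0, mean only |
|---|---|---|---|---|
| 0.5 | 0.750 | 0.667 | 11.1% | 0.917 |
| 0.6 | 0.640 | 0.550 | 14.1% | 0.750 |
| 0.7 | 0.510 | 0.424 | 17.0% | 0.574 |
| 0.8 | 0.360 | 0.289 | 19.8% | 0.389 |

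The last column is worse than the current plan in every row: 0.917/0.750 is 22% more residual variance at r = 0.5, and 0.389/0.360 is 8% more at r = 0.8. The mean no longer adjusts properly for the Day 0 value that was subtracted.

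**Case 2: the two pre-infusion values are closer to each other than to follow-up**

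| q | ρ = 0.5 | ρ = 0.6 | ρ = 0.7 |
|---|---|---|---|
| 0.8 | 3.7% | 6.3% | 10.7% |
| 0.9 | 1.8% | 3.0% | 5.1% |

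For example, with q = 0.8 and ρ = 0.7: 1 − 2(0.49)/1.8 = 0.4556, and 1 − 0.4556/0.51 = 10.7%.

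**Case 3: Day 0 is also the better predictor.** Take q = 0.85, ρ_S = 0.5 and ρ_D = 0.6. The explained part with both values is (0.25 + 0.36 − 0.51)/(1 − 0.7225) = 0.10/0.2775 = 0.3604, against 0.36 with Day 0 alone. The cut is 0.06%.

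**Cost.** A simple two-group model with one covariate leaves 93 − 3 = 90 residual degrees of freedom. One more covariate uses 1 of 90, about 1%.

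**Simulation** (62 and 31 subjects, 6,000 runs, both values as separate covariates). The variance of the treatment estimate fell by 10.4% at equal correlations of 0.5 and by 20.7% at 0.8. At ρ = 0.6 and q = 0.85 it fell by 2.7%; the closed form gives 1 − [1 − 2(0.36)/1.85]/0.64 = 4.6% before the cost of the extra covariate. The results agree with the formulas, allowing for that cost and simulation error.

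**The case against.** The strongest reply is that nothing here is wrong. The last value before infusion, used as baseline and covariate, is a conventional, unbiased and prespecified choice. The endpoint is secondary, tested at 0.05 without multiplicity control, and plays no part in declaring the trial a success. All of this stands and limits the point to an optional improvement.

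The reply on size also stands. Equal correlation is the favourable case. Samples at most about four weeks apart will usually agree with each other better than with values 6 or 12 months later, and the gain then shrinks. In Case 3 the extra degree of freedom costs slightly more than it returns.

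The formulas suit a linear model on the log scale. They do not carry over to raw percent change, one of the two forms SAP 9.5 describes, because there the Day 0 value is also the denominator.

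A reader might further infer that the two documents give conflicting NT-proBNP baselines, because Protocol 9.5.2 says "Baseline assessments are conducted during the" Screening visit while SAP 7.6 leads to Day 0. The documents do not support that. The sentence sits in the primary efficacy section, directly after the MRI infarct-size endpoint, whose only scheduled pre-infusion assessment is at screening. Protocol 9.6.2 refers to the baseline of whichever endpoint is analysed and leaves further detail to the SAP, and SAP 7.6 supplies a single rule. That rule already covers a missing Day 0 value.

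What the reply does not remove is that a prognostic value, already scheduled and collected, is left out of the model when including it costs almost nothing.

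**Conclusion.** The point holds as a small, optional gain in precision for the log-transformed NT-proBNP change. The cut in residual variance from entering both values is:
- 11 to 20% if all within-subject correlations are equal and lie between 0.5 and 0.8;
- about 2 to 11% if the two pre-infusion values correlate at 0.8 to 0.9 and each correlates at 0.5 to 0.7 with follow-up;
- near zero if Day 0 is also the better predictor.

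These correlations are assumptions, so no single percentage should be quoted as the loss. The figures are cuts in residual variance. It would be tempting to read 11 to 20% as the share of the achievable variance reduction that is given up, but with equal pre-post correlations that share is (1 − q)/2, which is 25% at q = 0.5 and 10% at q = 0.8, and so moves the other way. The point implies no bias, and it does not touch the primary analysis.

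**What to change.** Add to SAP 9.5, for the log-transformed NT-proBNP change that the protocol lists:
- The Day 0 pre-infusion value remains the baseline for the change score, as SAP 7.6 already implies.
- The log screening value and the log Day 0 value enter the model as two separate covariates.
- If one of the two is missing, the other is used in its place.
- The mean of the two is not used as the only covariate with a change score taken from Day 0.

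SAP 9.5 does not currently name the log-transformed endpoint, so the added text has to name it for the adjustment to have an analysis to attach to. The cost is one or two sentences before unblinding and one degree of freedom, about 1% with 93 completers. No new sample, visit or data field is needed.
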